Innovation – The GEMS study described above is one approach to identification of early MS, but it had several limitations. It used a pre-defined risk score, including a SNP analysis of just 64 SNPs, when more recent analysis suggests over 200 may be relevant. It employed a long, detailed, and expensive brain MRI, but did not include spine or FLAIR\* analysis. The cost limited participation. GEMS did not include potential immunological markers, markers of CNS damage (such as NFL or lipids), activity levels, or a detailed environmental screen. Due to privacy issues, they were unable to verify the MS diagnosis in FDRs. Finally, it was limited to 100 patients, of which only 65 (females only) were analyzed. Other studies (as yet unpublished) designed to look at risk factor algorithms for development of MS are employing larger numbers of patients, but minimal, if any, MRI analyses, no or minimal immunological or CNS damage markers, and no activity levels. Most importantly, they are using full clinical diagnosis of MS as the outcome measure, greatly limiting the number of “positive” patients, and biasing toward a much later time in the disease process. Thus, our study has great innovative value for several reasons:

- a. We will define pre-symptomatic MS in 300 FDRs using stringent MRI criteria, including FLAIR\* sequences, thus significantly increasing sensitivity and detection in the prodromal phase. Proband MS patients will be defined from our own population of MS patients known to fulfill formal diagnostic criteria for MS.
- b. We will analyze genetic, immunological, vitamin, lipid, viral, and CNS damage markers; activity levels; and a mood and cognitive screen, with the goal of defining an expanded risk stratification scheme, not a pre-defined one
- c. We will include a detailed environmental screen, employing approaches very similar to the DAISY study, and [name], lead epidemiologist in DAISY, will participate as a Co-PI.
- d. We will compare those FDRs with and without brain MRI abnormalities to each other, and to non-FDR controls (blood and environmental screen, not MRI)
- e. We will create a biobank of blood, both plasma and PBMCs, including pre-processed serum/plasma and RNA, allowing us to add to the risk stratification model over time.

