The sequences were specifically chosen to: a) screen brain with the greatest specificity (FLAIR\*); b) allow for later volumetric analysis of the brain; and c) use the most sensitive technique for cortical and subcortical brain lesions (3D-DIR).

**B. Description of Population to be Enrolled:** The population will be a total of 300 women and men, of all races and ethnicities, between the ages of 18-30, inclusive, who have no symptoms of MS, but have at least one FDR with documented MS fulfilling McDonald 2017 criteria. Up to 1000 will be screened for inclusion, but some will be excluded due to inability to undergo a brain/spine MRI or have blood drawn, lack of interest after discussion of study requirements, or symptoms concerning for MS (the latter will be referred to a qualified neurologist for evaluation). FDRs with one or more siblings/parents with MS will be included, and more than one FDR of a proband MS patient will be allowed. A control group (based on # of FDRs with positive MRIs - we anticipate 15-30) of age- and sex-matched controls who have no known family members with MS (out to first cousins and grandparents) will have blood drawn and fill out the environmental questionnaire, but will not undergo a brain MRI. The controls will be matched 1:1:1 for those FDRs with positive MRI scans suggesting pre-symptomatic MS and those age-and sex-matched FDRs who do NOT have positive MRI scans suggesting pre-symptomatic MS. The ages were specifically chosen so as to have a good opportunity to collect an adequate number of MRI-positive, asymptomatic participants prior to the known median age of MS clinical onset (30 years), but not so young as to lower the likelihood of detecting asymptomatic brain MRI lesions.

1. FDR Inclusion Criteria
  - a. Male and female
  - b. All races and ethnicities
  - c. Ages 18-30
  - d. Must have a parent, sibling or child with MS fulfilling McDonald 2017 criteria
  - e. No symptoms suggestive of MS on formal screen
  - f. Ability to undergo a non-contrast MRI and venipuncture, and perform an environmental screen, mood screen and cognitive test
2. FDR Exclusion Criteria
  - a. Symptoms suggestive of MS on formal screen
  - b. Prior diagnosis of autoimmune disease that may be associated with CNS dysfunction and MRI lesions, e.g. Sjogren's
3. Non-FDR Inclusion Criteria
  - a. Male and female
  - b. All races and ethnicities
  - c. Ages 18-30

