## **F. Data Analysis Plan: Statistical Approach**

- a. Based on previous studies, we estimate that 5-10% of the 300 FDRs (15-30) in our pilot study will exhibit an MRI endpoint. In order to test for associations with this endpoint to obtain valuable preliminary data, we will perform a nested case control study. We will match two controls per case based on age and sex: one group will be FDRs not fulfilling DIS on brain MRI; the second will be non-FDRs who are age- and sex-matched to FDRs who do, and do not, fulfill DIS on MRI scans. The non-FDRs will perform the environmental screen and undergo venipuncture for blood analysis identical to the other two groups, but will not have a MRI scan.
- b. Aim 1. Descriptive statistics

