- c. Aim 2. Association analyses; with individual factors and in a multiple risk factor analysis. In previous studies, HLA type, Vitamin D levels, Epstein Barr Virus exposure, smoking and early adult obesity have conferred a maximum odds ratio of 2-3 (many SNPs confer an odds ratio of 1.1-1.4) of developing MS when studied individually. In the GEMS study, participants were stratified into high and low risk categories based on a deep phenotyping of 64 SNPs, and environmental screen (including sex). Comparative analyses were performed on the high and low risk groups for both neurological exam and MRI measures. In this study, we plan to use the known risk factors, and add potential biomarkers (e.g. NfL, lipid levels) to define the risk of DIS in this population. For the power analysis we made the assumption that no single marker would exhibit an odds ratio greater than 2 for increased risk of DIS, and that all markers are additive. In this early proof of concept phase, with an estimated case sample size of 30 with 60 age- and sex-matched controls, our priori power analysis suggests an expected power ranging from 20-33% for risk factors such as smoking, obesity, and vitamin D deficiency. Using frequency and odds ratio from the GEMS study (OR = 2.9) we expect a power of 64% to detect an effect of HLA type risk. While this study will be statistically underpowered, and estimates will be imprecise, we expect that some results will have clinical significance. We plan to use these results and stored samples as the groundwork for larger, longitudinal, multi-site studies. These future studies will allow us to enroll samples sizes of greater than 500, necessary to reach 80-90% power. In reality, it is possible the effect some factors may depend on the levels of other factors. Example hypothesis that we will test: FDRs with DIS lesions are more likely to have been exposed to EBV as indicated by elevated EBV serology than FDRs of the same age and sex without DIS lesions. By extension, we will then define a risk score combining factors that are discriminatory, e.g. Vitamin D level, smoking, obesity, elevated NfL levels, impaired B cell anergy, and HLA type may each have a roughly 2 fold increased risk, whereas those with four of these factors have a six-fold increased risk of DIS on MRI.
- d. Aims 3 and 4 do not have statistical implications.

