## **G. Summarize Knowledge to be Gained:**

This is a highly innovative research protocol which seeks to duplicate the approach of the successful DAISY study, but in a MS population. We aim to define a set of environmental, genetic, lipid, neuroaxonal/myelin damage or immunological markers of earliest disease activity in MS. From this, we ultimately hope to develop a risk stratification algorithm for development of MS. This will allow for earliest possible intervention for this disabling disease. The purpose of Aim 4 will be to enhance the risk profile over time, as other potential, highly sensitive, precise biomarkers become available. One example is

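### To the extent that Aim 2 risk-score factors are kept or weighted because of the same 15-30 cases, their odds ratios are overstated on average, and the plan has no shrinkage or internal validation

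*Combined protocol and SAP*

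**What the plan says.** Section II, Aim 2, makes a risk factor score for lesions disseminated in space (DIS) a product of the study. Section V.F item a expects 5-10% of 300 first-degree relatives (FDRs), that is 15-30, to be cases, and states "We will match two controls per case based on age and sex". One control is an FDR without DIS, the other a non-FDR without MRI.

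Section V.F item c describes association analyses of single factors and a multiple-factor analysis. On inputs it says "we plan to use the known risk factors, and add potential biomarkers (e.g. NfL, lipid levels) to define the risk of DIS". On the score it says "we will then define a risk score combining factors that are discriminatory, e.g. Vitamin D level, smoking, obesity, elevated NfL levels", and it continues with HLA type and B cell anergy. Section III (Innovation, item b) describes the work "with the goal of defining an expanded risk stratification scheme, not a pre-defined one".

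The score is meant to live on. Section III (Innovation, item e) describes the biobank as "allowing us to add to the risk stratification model over time", and Section V.G says "The purpose of Aim 4 will be to enhance the risk profile over time".

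The caveat in Section V.F item c is: "While this study will be statistically underpowered, and estimates will be imprecise, we expect that some results will have clinical significance".

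No section defines what counts as discriminatory, how many candidates there are, or how factors are weighted. None mentions shrinkage, resampling, a hold-out sample or an independent test of the score. No performance measure is named. The only validation mentioned is of questionnaires.

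**The concern.** A factor that has to look discriminatory before it enters the score enters more often when chance has pushed its estimate up. At the power the plan states for typical factors (20-33%), most samples do not let a real effect through, and those that do carry estimates above the truth on average. Describing the score in the same people adds a second layer, because weights fitted to those people also fit their noise. This is a systematic shift. The words underpowered and imprecise describe scatter around the right value, so they do not warn the reader of it.

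At stake are the score named in Aim 2 and what is built on it. Section V.F item c makes these results the groundwork for larger studies, and Sections III and V.G foresee extending the model. Later versions would start from odds ratios (ORs) that are too large on average, and a score with no predictive value could look useful.

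**Working it through.** **Inputs from the plan.** 15-30 cases and two controls per case (V.F item a); 30 cases v 60 controls, single-marker OR at most 2, stated power 20-33%, and HLA at OR 2.9 with stated power 64% (V.F item c).

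**Assumed, because the plan is silent.** Two-sided p<0.05 as the entry rule; exposure in controls p0 = 20-40%; independent binary factors; log-OR weights; 8 candidates (the factors named in V.F item c: HLA, vitamin D, EBV, smoking, obesity, NfL, lipids, B cell anergy), with 6 and 20 as a range.

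**Step 1: reproduce the stated power.**
p1 = OR·p0 / (1 − p0 + OR·p0); p̄ = (30·p1 + 60·p0)/90.
Power = Φ{[(p1 − p0) − 1.96·√(p̄(1−p̄)(1/30+1/60))] / √(p1(1−p1)/30 + p0(1−p0)/60)}.
For OR 2 and p0 = 0.30: p1 = 0.60/1.30 = 0.462 and p̄ = 0.354. Power = Φ[(0.162 − 1.96·0.107)/0.109] = Φ(−0.44) = 33%. At p0 = 10% it is 21%, and at 20% it is 29%. For OR 2.9 it is 63% at p0 = 25% and 65% at 30%. The plan's 20-33% and 64% are reproduced.

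**Step 2: estimate given that the factor is kept.** Simulated 2×2 tables, unmatched Pearson test, factor kept if p<0.05 in the risk direction, 0.5 added per cell to the OR. Ranges cover p0 = 20-40%.

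| Cases v controls | True OR | Median OR if kept |
|---|---|---|
| 30 v 60 | 2 | 3.1-3.3 |
| 15 v 30 | 2 | 4.6-5.3 |
| 30 v 270 (all MRI-negative FDRs) | 2 | 2.7-2.8 |
| 15 v 285 (all MRI-negative FDRs) | 2 | 3.5-3.7 |
| 30 v 60 (HLA) | 2.9 | 3.5-3.7 |
| 15 v 30 (HLA) | 2.9 | about 5 |

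With a matched (conditional) analysis the first two rows become 3.2-3.6 and 5.3-6.3. With entry at p<0.10 (conditional) they become 2.9-3.1 and 4.3-5.0.

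**Step 3: stress test with no true effect.** The chance that at least one of K unrelated candidates passes is about 1 − 0.95^K: 27% for K = 6, 34% for K = 8, 64% for K = 20. In simulation with K = 8 a score forms in about a third of studies. Its mean apparent area under the ROC curve (AUC) is 0.62-0.64 (30 v 60) or 0.66-0.69 (15 v 30), against 0.50 in new data.

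**Step 4: some real effects.** With 4 of 8 factors at OR 2, apparent AUC is 0.67-0.70 against 0.58-0.60 in new data (30 v 60), and 0.70-0.73 against 0.56-0.58 (15 v 30).

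**Step 5: is a fixed list enough?** Not if the weights are still estimated. Six pre-chosen factors, all truly at OR 2 with p0 = 30% and no selection, give apparent AUC 0.76 against 0.69 in new data (30 v 60).

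**Step 6: does the remedy work?** Ridge conditional logistic regression with a fixed penalty and 8 binary candidates, AUC taken only from left-out matched sets:
- No effect: 0.49-0.51.
- 4 of 8 at OR 2, 30 sets: 0.61-0.64, against 0.62-0.64 in new data.
- 4 of 8 at OR 2, 15 sets: 0.58-0.62, against 0.60-0.62 in new data.
- Ridge without leaving sets out, no effect: 0.67-0.75, so shrinkage alone does not suffice.
- No effect, with an assumed 5 pairs of sibling cases in 30 sets or 3 in 15: leaving out single sets reads 0.52-0.53; leaving out linked sets together reads 0.50. This matters because Section V.B says "more than one FDR of a proband MS patient will be allowed".

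This check did not cover data-driven tuning or a candidate list on the scale of the SNP panel.

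**The case against.** The strongest reply is that data-driven selection is only one reading. Aim 2 speaks of including all relevant markers, Section V.F item c says known risk factors will be used, and the sentence on the score is framed by an example. A plain count of factors included on prior evidence alone would not carry this bias. That stands, and it is why the point is conditional. It does not remove the point: the same item forms the score from discriminatory factors after testing them, adds new biomarkers, and Section III rules out a pre-defined scheme.

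Second, the plan names no performance measure. A reader might infer that an inflated AUC will be published; the documents do not say so. The AUC figures show what would happen if one were reported.

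Third, the size depends on choices the plan does not make. Section V.F item a describes a nested case-control study, while Section V.C item 6 calls it case-cohort. If all MRI-negative FDRs serve as controls for Visit 1 markers, the overstatement shrinks but remains. HLA, the best-powered factor, is inflated proportionately less. Treating every candidate as noise is a stress test, given the prior ORs of up to 2-3 for MS that the plan cites.

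Fourth, the plan is candid that it is a proof of concept that will not settle the question (Section V.E). This limits the consequence, but a label of imprecision does not correct a bias.

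**Conclusion.** The concern holds in conditional form. To the extent that factors are kept or weighted because of these data, the ORs and any reported performance are overstated on average. With entry at p<0.05, 20-40% exposure and an unmatched test, a true OR of 2 is kept at a median of about 3.1-3.3 (30 v 60) or 4.6-5.3 (15 v 30), and 2.7-2.8 if all MRI-negative FDRs are controls (30 v 270). The direction was the same in every data-driven scenario run; the sizes are illustrative.

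Three stronger readings are not supported. The overstatement is an average and need not appear in every realised score. It does not reach clinical decisions, because referral follows the MRI (Section V.C item 4) and no decision in the protocol uses the score. It does not show that later studies would be undersized, because the figure of more than 500 is stated separately from any result of this study. This is a worthwhile correction to a pilot, not a fault that undermines it.

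**What to change.** In Section V.F item c, replace the rule of combining discriminatory factors with four statements:

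1. The candidate factors are listed before any marker is compared with MRI status. Their weights are still learned from the data, so the scheme is not pre-defined.
2. The score is fitted with a shrinkage (penalised) model that respects the matching, instead of combining factors screened one at a time. Ridge conditional logistic regression is one example; another shrinkage method would serve.
3. Any discrimination reported comes only from internal validation that leaves out whole matched sets, keeps relatives of one proband together, and repeats all selection and tuning in each refit. It is shown separately against DIS-negative FDRs and against non-FDRs. At most a calibration slope is reported, because absolute risk cannot be estimated from the matched design.
4. The score is labelled exploratory until tested in independent data.

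Also reconcile nested case-control (V.F item a) with case-cohort (V.C item 6), since this sets which controls are used.

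The cost is plan wording and analyst time, with no extra participants, assays or visits. The downside is that reported discrimination will be lower and still imprecise: in simulation the SD of the AUC is about 0.08-0.12 per control group with 30 sets and 0.14-0.16 with 15. In this study it will rarely separate a modestly useful score from a useless one.

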## **G. Summarize Knowledge to be Gained:**

This is a highly innovative research protocol which seeks to duplicate the approach of the successful DAISY study, but in a MS population. We aim to define a set of environmental, genetic, lipid, neuroaxonal/myelin damage or immunological markers of earliest disease activity in MS. From this, we ultimately hope to develop a risk stratification algorithm for development of MS. This will allow for earliest possible intervention for this disabling disease. The purpose of Aim 4 will be to enhance the risk profile over time, as other potential, highly sensitive, precise biomarkers become available. One example is

microRNA (miRNA), which are a class of small (~21-25 nucleotides), noncoding RNAs. These are very important in posttranscriptional regulatory processes. MiRNA's may directly and indirectly promote neurodegenerative action through a variety of pathways. MiR-155, known to be upregulated in MS, and silences CD47, a protein involved in phagocytic signaling processes that block macrophage activation. MiRNA's may contribute to disease progression by driving differentiation of Th1 and Th17, known pathogenic T-cell subsets. MiRNA may have potential as a tool for relapse prediction, distinguishing different subtypes of MS (i.e. RRMS vs. PPMS vs. SPMS), and determine disease progression. MiRNA's may have potential as therapeutic targets for controlling disease activity. Untreated MS patients display elevated levels of miR-126 relative to healthy controls. After these patients underwent DMT treatment, levels of miR-126 decreased to similar amounts observed in controls. Non-invasiveness, easy analysis, and high-stability make miRNA a desirable biomarker for disease prediction. However, one miRNA sampled from various compartments (plasma, serum, lymphocytes) yields significantly different results, contributing to the complexity of comparing results across studies. Additionally, RNA extraction, miRNA measurement, and analyzation do not have a standardized protocol, resulting in heterogeneous results across different studies. As novel, consistent, and standardized techniques become available, miRNA expression studies with longitudinal design at a large site with control comparators may allow for insight on miRNA's ability to predict development of MS, relapses, and even disease subtype.

